10.1.2 Serious adverse events

An SAE is defined as any adverse event [appearance of (or worsening of any pre-existing)] undesirable sign(s), symptom(s) or medical conditions(s) which meets any one of the following criteria:

1. Fatal
2. Life-threatening

Life-threatening in the context of a SAE refers to a reaction in which the subject was at risk of death at the time of the reaction; it does not refer to a reaction that hypothetically might have caused death if it were more severe (please refer to the ICH-E2D Guidelines).

1. Results in persistent or significant disability/incapacity
2. Constitutes a congenital anomaly/birth defect
3. Requires inpatient hospitalization or prolongation of existing hospitalization, unless hospitalization is for:
 1. Routine treatment or monitoring of the studied indication, not associated with any deterioration in condition
 2. Elective or pre-planned treatment for a pre-existing condition that is unrelated to the indication under study and has not worsened since signing the informed consent
 3. Social reasons and respite care in the absence of any deterioration in the subject's general condition
 4. Treatment on an emergency outpatient basis for an event not fulfilling any of the definitions of a SAE given above and not resulting in hospital admission
 5. Occurrence of chronic GvHD
 6. Progression/relapse of underlying hematologic disease (including fatal outcomes) as defined in [Section 16.3 Appendix 3](#).
 7. Is medically significant, e.g. defined as an event that jeopardizes the subject or may require medical or surgical intervention to prevent one of the outcomes listed above

Medical and scientific judgment should be exercised in deciding whether other situations should be considered serious reactions, such as important medical events that might not be immediately life threatening or result in death or hospitalization but might jeopardize the subject or might require intervention to prevent one of the other outcomes listed above. Such events should be considered as “medically significant”. Examples of such events are intensive treatment in an emergency room or at home for allergic bronchospasm, blood dyscrasias or convulsions that do not result in hospitalization or development of dependency or abuse.

All malignant neoplasms will be assessed as serious under “medically significant” if other seriousness criteria are not met and the malignant neoplasm is not a disease progression of the study indication.

Any suspected transmission via a medicinal product of an infectious agent is also considered a serious adverse reaction.

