Response to study treatment will be assessed by the investigator at every visit during the treatment period ([Section 8.3](#)). Response assessment by the investigator at Day 28 and at Day 56 will support respectively, the primary and key secondary endpoint assessments for this trial.

Patients will be also monitored for aGvHD flares occurring during steroid, CNI, and ruxolitinib taper.

Investigator should carefully record any action taken to manage aGvHD including start of tapering, initiation of any new systemic therapy, re-escalation of corticosteroids and the re-escalated steroid dose, and steroid taper failure.

The data should be entered in the appropriate CRFs. Worsening of aGvHD, including occurrence of GvHD flare will be reported on appropriate specific CRF and, not as an adverse event ([Section 10.1.1](#)).

Note: Additional assessments may be done as per institutional guidelines at investigator's discretion. aGvHD assessments performed at unscheduled visit and leading to a change in patient's management or a change in patient's response should be recorded in the CRF.

Table 8-3 Response assessment

Efficacy assessments:

aGvHD response assessment will be made with respect to the organ stage at screening and Day 1:

4. **Complete response** is defined as a score of 0 for the aGvHD grading in all evaluable organs that indicates complete resolution of all signs and symptoms of aGvHD in all evaluable organs without administration of additional systemic therapy for any earlier progression, mixed response or non-response of aGvHD.
5. **Partial response** is defined as improvement of 1 stage in 1 or more organs involved with aGvHD signs or symptoms without progression in other organs or sites without administration of additional systemic therapy for an earlier progression, mixed response or non-response of aGvHD.
6. **Lack of response** is defined as no response, mixed response, or progression.
7. **No response** is defined as absence of improvement in any organ involved by aGvHD, without worsening in any involved organ.
8. **Mixed response** is defined as improvement of at least 1 stage in the severity of aGvHD in one organ accompanied by progression in another organ or development of signs or symptoms of aGvHD in a new organ.
9. **Progression** is defined as worsening in 1 or more organs by 1 or more stages without improvement in any involved organ.

Patients requiring additional systemic therapy for aGvHD will be classified as non-responders.

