4. Action taken with respect to study treatment (dose increased, dose not changed, dose reduced, drug interrupted, drug withdrawn, not applicable, unknown)
5. Whether Concomitant or additional treatment given due to this adverse event (yes / no)
6. Whether it is serious, where a serious adverse event (SAE) is defined as in [Section 10.1.2](#) and which seriousness criteria have been met

If the event worsens the event should be reported a second time in the eCRF noting the start date when the event worsens in toxicity. For grade 3 and 4 adverse events only, if improvement to a lower grade is determined a new entry for this event should be reported in the eCRF noting the start date when the event improved from having been Grade 3 or Grade 4.

All adverse events should be treated appropriately. If a concomitant medication or non-drug therapy is given, this action should be recorded on the Adverse Event eCRF.

Once an adverse event is detected, it should be followed until its resolution or until it is judged to be permanent, and assessment should be made at each visit (or more frequently, if necessary) of any changes in severity, the suspected relationship to the study treatment, the interventions required to treat it, and the outcome.

The following events, which are components of study endpoints: worsening of study indication (aGvHD) including occurrence of aGvHD flare as defined in [Section 6.1.5.1.1](#), occurrence of chronic GvHD, or progression/relapse of underlying hematologic disease (including fatal outcomes) as defined in [Section 16.3](#) (Appendix 3), should not be reported as a serious adverse event and will be reported on specific CRFs other than AE eCRF.

Adverse events separate from the events listed above (example, deep vein thrombosis at the time of progression or hemoptysis concurrent with finding of disease progression) will be reported as per usual guidelines used for such events with proper attribution regarding relatedness to the drug.

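### Protocol 10.1.2 omits worsening or flare of acute GvHD from its SAE hospitalization exceptions, although 10.1.1 and 8.4.1.2 keep those events out of SAE and AE reporting

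*Protocol*

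**What the plan says.** - **Protocol 10.1.1** lists three events that are components of study endpoints. The first is "worsening of study indication (aGvHD) including occurrence of aGvHD flare as defined in" the flare section; the others are chronic GvHD and progression or relapse of the hematologic disease. These "should not be reported as a serious adverse event and will be reported on specific CRFs other than AE eCRF". The same section sends the decision on whether an event is serious to 10.1.2.
- **Protocol 8.4.1.2** agrees: "Worsening of aGvHD, including occurrence of GvHD flare will be reported on appropriate specific CRF and, not as an adverse event".
- **Protocol 10.1.2** starts from any adverse event, including worsening of a pre-existing condition. One seriousness criterion is: "Requires inpatient hospitalization or prolongation of existing hospitalization, unless hospitalization is for" one of a list of reasons. That list includes "Routine treatment or monitoring of the studied indication, not associated with any deterioration in condition", "Occurrence of chronic GvHD" and "Progression/relapse of underlying hematologic disease (including fatal outcomes) as defined in" Appendix 3. Worsening or flare of acute GvHD is not in it.
- **Protocol 10.1.3** requires every SAE, whatever its suspected cause, to reach the sponsor within 24 hours. It repeats no exemption for endpoint events.
- **SAP 3.8.1** summarizes all on-treatment AEs, including by seriousness and by fatal outcome. **SAP 3.2.1** repeats SAE tables by age group, formulation and diagnosis. **SAP 3.8.1.2** adds the public disclosure tables. The visible text gives no rule for acute GvHD events that were entered as SAEs.

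**The concern.** Deterioration of acute GvHD is a foreseeable event in this trial. The protocol gives rules for flare and for lack of response (6.1.5, 6.1.5.1.1), and it expects flare after abrupt interruption of ruxolitinib (6.5.2.1.1). When a child is admitted for it, a site working from 10.1.1 or 8.4.1.2 uses the disease-specific form only. A site working from 10.1.2 and 10.1.3 may file an SAE. The same clinical event can then enter the SAE tables at one center and not at another.

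The trial has one arm, so there is no control group in which such differences would tend to balance. The overall SAE proportion would depend partly on which section a site followed, and some of what it counts as toxicity would be disease activity already captured by the efficacy endpoints.

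**Working it through.** The plan states no figure on this point, so there is none to reproduce. The check is a comparison of texts, followed by a calculation of scale.

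**Step 1. The three endpoint events, section by section**

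| Endpoint event | 8.4.1 | 10.1.1 | 10.1.2 hospitalization exceptions |
|---|---|---|---|
| Worsening or flare of acute GvHD | Not an AE (8.4.1.2) | Not an SAE | Absent; care for the studied indication is exempt only if there is no deterioration |
| Chronic GvHD | Not an AE (8.4.1.3) | Not an SAE | Listed |
| Hematologic relapse or progression | Not an AE (8.4.1.5) | Not an SAE | Listed, fatal outcomes included |

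Two of the three exemptions are carried into 10.1.2. The third is missing, and the only exception that touches the studied indication excludes deterioration.

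**Step 2. One admission under each reading**

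Take a child admitted because acute GvHD has progressed.
- Under 10.1.1 and 8.4.1.2 it goes on the specific form, with no AE and no SAE.
- Under 10.1.2 a pre-existing condition has worsened, admission was needed, and no exception fits. With 10.1.3, it is reportable within 24 hours.

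**Step 3. Fatal outcomes**

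In both 10.1.1 and 10.1.2 the mention of fatal outcomes is attached to the hematologic relapse item. SAP 3.7.1 expects death due to acute GvHD to be identified from the death form. Neither document says plainly whether such a death is also a fatal SAE, yet SAP 3.8.1 and 3.8.1.2 tabulate fatal AEs and deaths resulting from SAEs.

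**Step 4. Scale**

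Inputs, from the Amendment 3 rationale: 45 patients enrolled, with 18, 12 and 15 in Groups 1, 2 and 3. I assume all were dosed and so belong to the Safety Set. Let k be the number of patients whose only SAE would be an admission for worsening acute GvHD. The any-SAE proportion then differs between the two readings by k/45.

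- k = 1: 1/45 = 2.2 percentage points
- k = 5: 5/45 = 11.1 points
- k = 9: 9/45 = 20.0 points

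One patient within an age group: 1/18 = 5.6 points (Group 1), 1/12 = 8.3 points (Group 2), 1/15 = 6.7 points (Group 3).

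The documents give no value for k. The values 5 and 9 are illustrations, not estimates.

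**The case against.** The best answer is that the protocol, read as a whole, already settles the matter. An SAE must first be an adverse event, and 8.4.1.2 says worsening acute GvHD is not reported as one. 10.1.1 names the event and gives it a specific rule, while 10.1.2 is a general list that reaches the opposite result only through an omission and a conditional exception. This largely stands as an account of intent: non-reporting was probably meant. It does not remove the conflict. 10.1.1 itself refers seriousness to 10.1.2, and repeating two exemptions while leaving out the third invites a careful site with a 24-hour duty to report.

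Three further replies have force.
- SAE tables by preferred term and the AE listings would show events coded to GvHD. A reader might infer that such events disappear into the safety data; they do not. The problem lies in aggregate rows, such as patients with any SAE.
- The trial is descriptive and tests no hypothesis, so no between-arm comparison is biased.
- SAE submission instructions are in an investigator folder that is not among the documents. Actual divergence between sites is therefore possible but not shown. Part of SAP 3.8.1.1 is redacted and cannot be checked.

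**Conclusion.** The inconsistency is in the current text and should be reconciled. The protocol does not state outright that admission for worsening acute GvHD is an SAE; 10.1.2 and 10.1.3 allow that reading, while 10.1.1 and 8.4.1.2 point the other way. A reader might also take 10.1.1 as an absolute prohibition, but its wording is advisory.

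The supportable size is 2.2 percentage points of the any-SAE proportion for each patient whose only SAE is such an admission, and 5.6 to 8.3 points within an age group, if all 45 were dosed. It is tempting to go further and derive a count from Day 28 non-response: 45 × (1 − 0.80) = 9 at the planning response rate, or 45 × (1 − 0.62) = 17.1 at the rate cited from the phase III trial. The documents do not support that, for four reasons:
- Lack of response includes patients with no worsening in any organ, and missing assessments and early discontinuation also count as non-response.
- Responders who flare later are left out.
- The 62% comes from steroid-refractory patients aged 12 or older.
- No admission rate is given, and a patient who already has another SAE does not change the proportion.

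The primary endpoint is unaffected.

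**What to change.** 1. **Protocol.** Reconcile 10.1.1, 10.1.2 and 8.4.1.2 so that they state one reporting rule for worsening or flare of acute GvHD, fatal outcomes included. Either direction resolves the conflict, provided all three sections agree.
2. **SAP.** Enrollment is complete, so a wording change does little for events already recorded. Flag SAEs coded to acute GvHD terms and present the overall SAE summary and the fatal-SAE summary with and without them. The row without these terms does not depend on which section a site followed, provided the events were coded to a GvHD diagnosis and not to single symptoms. Repeating every SAE table is unnecessary, because the preferred-term tables and listings already show these events.

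The cost is one protocol sentence and one extra table row or variant, from data already collected.

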10.1.3 SAE reporting

To ensure patient safety, every SAE, regardless of suspected causality, occurring after the patient has provided study informed consent and until at least 30 days after the patient has

stopped study treatment must be reported to Novartis safety immediately, without undue delay, under no circumstances later than within 24 hours of learning of its occurrence.

Any additional information for the SAE including complications, progression of the initial SAE, and recurrent episodes must be reported as follow-up to the original episode within 24 hours of the investigator receiving the follow-up information. An SAE occurring at a different time interval or otherwise considered completely unrelated to a previously reported one should be reported separately as a new event.

Information about all SAEs is collected and recorded on the Serious Adverse Event Report Form; all applicable sections of the form must be completed in order to provide a clinically thorough report. The investigator must assess and record the relationship of each SAE to each specific study treatment (if there is more than one study treatment), complete the SAE Report Form in English, and submit the completed form within 24 hours to Novartis. Detailed instructions regarding the SAE submission process and requirements for signatures are to be found in the investigator folder provided to each site.

Follow-up information is submitted in the same way as the original SAE Report. Each re-occurrence, complication, or progression of the original event should be reported as a follow-up to that event regardless of when it occurs. The follow-up information should describe whether the event has resolved or continues, if and how it was treated, and whether the patient continued or withdrew from study participation.

If the SAE is not previously documented in the Investigator's Brochure (new occurrence) and is thought to be related to the Novartis study treatment, a chief medical office and patient safety (CMO & PS) department associate may urgently require further information from the investigator for Health Authority reporting. Novartis may need to issue an Investigator Notification (IN), to inform all investigators involved in any study with the same drug that this SAE has been reported. Suspected Unexpected Serious Adverse Reactions (SUSARs) will be collected and reported to the competent authorities and relevant ethics committees in accordance with Directive 2001/20/EC or as per national regulatory requirements in participating countries.

10.1.4 Pregnancy reporting

To ensure patient safety, each pregnancy occurring while the patient is on study treatment must be reported to Novartis within 24 hours of learning of its occurrence. The pregnancy must be followed up to determine outcome, including spontaneous or voluntary termination, details of the birth, and the presence or absence of any birth defects, congenital abnormalities, or maternal and/or newborn complications. It is mandatory to follow-up at three months and at 12 months after delivery for all cases of live birth to collect information on the status of the baby and information on any development issues or abnormalities that are not readily apparent at birth.

Pregnancy should be recorded on a Clinical Trial Pregnancy Form and reported by the investigator to the oncology Novartis Chief Medical Office and Patient Safety (CMO&PS).

Pregnancy follow-up should be recorded on the same form and should include an assessment of the possible relationship to the study treatment and any pregnancy outcome. Any SAE experienced during pregnancy must be reported on the SAE Report Form.

10.1.5 Reporting of study treatment errors including misuse/abuse

Not applicable

10.1.6 Laboratory Test Abnormalities

Laboratory abnormalities that constitute an Adverse event in their own right (are considered clinically significant, induce clinical signs or symptoms, require concomitant therapy or require changes in study treatment), should be recorded on the Adverse Events CRF. Whenever possible, a diagnosis, rather than a symptom should be provided (e.g. anemia instead of low hemoglobin). Laboratory abnormalities that meet the criteria for Adverse Events should be followed until they have returned to normal or an adequate explanation of the abnormality is found. When an abnormal laboratory or test result corresponds to a sign/symptom of an already reported adverse event, it is not necessary to separately record the lab/test result as an additional event.

Laboratory abnormalities, that do not meet the definition of an adverse event, should not be reported as adverse events. A Grade 3 or 4 event (severe) as per CTCAE does not automatically indicate a SAE unless it meets the definition of serious as defined below and/or as per investigator's discretion. A dose hold or medication for the lab abnormality may be required by the protocol in which case the lab abnormality would still, by definition, be an adverse event and must be reported as such.

10.1.7 Adverse events of special interest

Please refer to the ruxolitinib [\[Investigator Brochure\]](#) for safety information and selected adverse events, or the product label as applicable.

Adverse events of special interest (AESI) are selected categories of risks consisting of pooled AEs that are similar in nature, for which there is a specific clinical interest as a result of signals identified during the conduct of earlier trials with ruxolitinib. Such events on the basis of an ongoing review of the safety data and discussed in detail in the [\[Clinical Summary Preparation Document, RMP Pooling Plan and Statistical Methodology\]](#).

10.2 Additional Safety Monitoring

10.2.1 Liver safety monitoring

For liver safety monitoring guidelines, refer to [Section 6.5.3.1](#).

10.3 Committees

10.3.1 Data Monitoring Committee

This study will institute a data monitoring committee (DMC) which will function independently of all other individuals associated with the conduct of this clinical trial, including the site investigators participating in the study. The DMC will be constituted prior to the first patient

receiving treatment. The DMC will be responsible to review safety data approximately every 6 months during the Ph II (after the first patient has started study treatment). Additionally, during the Phase I, the DMC will review each age group data to determine an age appropriate RP2D. This data will include all PK data, safety, and activity data which will be collected over the first 28 days of the Phase I for that age group under review. There may be additional DMC reviews based on enrollment in each group in the Phase I for adequate and timely assessment of the age-appropriate RP2D. This includes but does not limit the role of the DMC to evaluate these and additional activity data and to provide recommendations to the sponsor to continue modify or stop the study early. The DMC will make a recommendation as to whether the safety and activity data is supportive of enrolling Group 4 into this trial.

Specific details regarding composition, responsibilities, data monitoring and meeting frequency, and documentation of DMC reports, minutes, and recommendations will be described in a separate charter that is established between the sponsor and the DMC.

10.3.2 Steering Committee

A Steering Committee (SC) will be established for this study. Further details on the functions and responsibilities will be outlined in the Steering Committee charter.

11 Data Collection and Database management

11.1 Data collection

For studies using Electronic Data Capture (EDC), the designated investigator staff will enter the data required by the protocol into the eCRF. The eCRFs have been built using fully validated secure web-enabled software that conforms to 21 CFR Part 11 requirements. Investigator site staff will not be given access to the EDC system until they have been trained. Automatic validation programs check for data discrepancies in the eCRFs and, allow modification or verification of the entered data by the investigator staff.

The Principal Investigator is responsible for assuring that the data entered into eCRF is complete, accurate, and that entry and updates are performed in a timely manner.

Blood samples for Biomarker and PK samples and/or data will be processed centrally and the results will be sent electronically to Novartis as described in the Data Transfer Specification.

11.2 Database management and quality control

For studies using eCRFs, Novartis personnel (or designated Clinical Research Organization [CRO]) will review the data entered by investigational staff for completeness and accuracy. Electronic data queries stating the nature of the problem and requesting clarification will be created for discrepancies and missing values and sent to the investigational site via the EDC system. Designated investigator site staff are required to respond promptly to queries and to make any necessary changes to the data.

Concomitant treatments and prior medications entered into the database will be coded using the WHO Drug Reference List, which employs the Anatomical Therapeutic Chemical classification system. Medical history/current medical conditions and adverse events will be coded using the Medical dictionary for regulatory activities (MedDRA) terminology.

Biomarker and PK samples and/or data will be processed centrally, and the results will be sent electronically to Novartis (or a designated CRO).

Data about all study treatments dispensed to the patient and all IRT assigned dosage changes will be tracked using an Interactive Response Technology. The system will be supplied by a vendor(s), who will also manage the database. The data will be sent electronically to Novartis personnel (or designated CRO).

The occurrence of any protocol violations will be determined. After these actions have been completed and the data has been verified to be complete and accurate, the database will be declared locked and made available for data analysis. Authorization is required prior to making any database changes to locked data, by joint written agreement between the Global Head of Biostatistics and Data Management and the Global Head of Clinical Development.

For EDC studies, after database lock, the investigator will receive a CD-ROM or paper copies of the patient data for archiving at the investigational site.

